Appendix 3. Endpoint Algorithm Development Plan

Figure 5. Development and Validation of Primary Endpoint Algorithms

In the first phase of the validation study, the Sponsor will develop an initial, proposed claim-based algorithm for each primary endpoint (Algorithm 1). Algorithms will be informed by the published literature and consultation with clinical experts having current experience managing these conditions in clinical practice in order that clinically sensible markers of care may be included. The Sponsor will use the algorithm to identify potential cases among women with at least one prescription of E+P HRT enrolled in the HIRD prior to the start of the study period. From the potential cases identified by applying the algorithm to this population, a random sample of 200 women will be selected for whom medical records will be reviewed for each outcome (ie, endometrial cancer and endometrial hyperplasia). This training dataset will undergo adjudication by the clinical panel, and will then be used to assess the PPV of the preliminary algorithm and to construct an analytic file to be used for predictive modeling. The algorithm (Algorithm 2) will then be optimized by developing a predictive model using machine learning to associate confirmed case status with data in the HIRD.

The Sponsor will use boosted regression techniques that have been used to improve the performance of logistic regression in computing propensity scores for predictive modeling.^{11,12} The model will be used to identify predictors in the HIRD and to weight each of the predictors according to their empirical importance. The model will assign to each woman in the population a probability of being a confirmed case. Analyses will be conducted

using Receiver Operating Characteristic (ROC) curves to assign a threshold probability (10). A second set of 200 medical records will then be obtained by randomly selecting 200 women meeting the refined, score-based algorithm from the population of women using E+P HRT prior to the study period. This validation dataset will be used to assess the PPV of Algorithm 2 (1). The PPV will be calculated as the number of algorithm-identified events confirmed as true cases via medical record review divided by the total number of algorithm-identified events that were evaluated, and will be presented with its exact binomial CI. The validated algorithms will then be used in the study analyses to identify the primary endpoints of interest, and sensitivity analyses will be used to assess the impact of misclassification based on algorithm performance characteristics such as PPV. Additional operational details pertaining to the validation process will be described in a separate Endpoint Algorithm Development Plan.

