7.2.1. Inclusion Criteria

All patients identified in the HIRD who have received a prescription for *Duavee* or E+P HRT since May 2014 (date of first commercial availability in the US), and have a baseline period (e.g., 6 or 12 months to be determined by a priori analyses) prior to their first study medicine prescription, will be included in this study. Codes for *Duavee* and specific E+P HRT products are listed in Appendix 2.

- To be included in the main analyses, patients need to be new initiators of *Duavee* or E+P HRT as evidenced by a sufficient baseline period (e.g., 6 or 12 months to be determined using a priori analyses) prior to their first study drug prescription with no prior use of either *Duavee* or E+P HRT.
- The duration of the baseline period will be determined prior to the start of the analysis. The analysis will assess the distribution of continuous enrollment prior to the first dispensing of *Duavee* among the exposed patients. Selection of a threshold will balance inclusion of as many *Duavee* users as is feasible with the need to ensure appropriate capture of baseline covariates among the included patients.
- Sub-analyses will be performed for those with either (1) use of E+P HRT (i.e., not new initiators), or (2) unopposed estrogen in their baseline period. See Figure 4 in Section [Section 7.8](#) for the flow of patients to the separate analyses.

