Specific data in the HIRD include enrollment data, medical care, prescription drug use, and health care utilization that can be tracked for each individual throughout the course of their enrollment in the selected health plans. Diagnoses and procedures for both outpatient and inpatient visits/stays are identified by ICD-9-CM diagnostic, ICD-9-CM procedure, CPT, and HCPCS codes. Outpatient pharmacy claims are captured by National Drug Codes (NDCs). Physician, specialist, and emergency room visits, as well as hospital stays, are captured in the database through ICD-9-CM diagnostic, ICD-9-CM procedure, CPT procedures, HCPCS, Uniform Billing Code of 1992 (UB-92) revenue (eg, room and board), and place of service codes. Information on physician specialty and laboratory result data are also retained in the database. The claims data in the HIRD also contain information necessary for economic analyses for both medical and pharmacy claims, including amounts charged to the provider and facility, amounts paid by the health plan and member (e.g., co-payments and deductibles), and coordination of benefits amounts.

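### The model-based score that defines the primary endpoints is developed only in E+P users and is not barred from using hormone-dispensing variables, so event detection could differ between the cohorts

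*Protocol*

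**What the plan says.** Appendix 3 describes two steps for each primary endpoint. An initial claims algorithm, informed by the literature and clinical experts "in order that clinically sensible markers of care may be included", identifies "potential cases among women with at least one prescription of E+P HRT enrolled in the HIRD prior to the start of the study period". From these, "a random sample of 200 women will be selected for whom medical records will be reviewed for each outcome". The adjudicated records then train Algorithm 2, which is to be "optimized by developing a predictive model using machine learning to associate confirmed case status with data in the HIRD". On the choice of variables the text says: "The model will be used to identify predictors in the HIRD and to weight each of the predictors according to their empirical importance". A ROC analysis sets the threshold.

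A second set of 200 records, again from women using E+P HRT before the study period, is used to estimate PPV. The validated algorithm then identifies the primary endpoints in the study analyses. Further operational details of the validation are left to a separate Endpoint Algorithm Development Plan.

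Four other places bear on this:
- Section 7.4.1 lists pharmacy data among the HIRD contents: "Outpatient pharmacy claims are captured by National Drug Codes".
- Section 7.2.1 gives May 2014, the start of the study period, as the "date of first commercial availability in the US".
- Under Sections 7.2.1 and 7.2.2, women with baseline E+P use are left out of the main analysis. Under Section 7.1, a Duavee user's follow-up is censored when she switches to E+P.
- Section 7.7.4 corrects each primary-endpoint incidence rate by multiplying observed cases by the PPV point estimate.

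**The concern.** An outcome definition should not depend on exposure. Here a data-driven model picks the variables that define the outcome, the data it may draw on include drug dispensing, and every woman it learns from used the comparator. If, among E+P users, the number of fills or stopping treatment helps to separate confirmed from unconfirmed cases, the model can use it.

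Applied to a Duavee user, such a variable may be absent or may carry a different meaning. Two women with the same diagnoses, biopsies and surgery could then fall on different sides of the threshold because of the drug they started.

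That would be differential outcome misclassification in the main comparison of a study set up to assess endometrial safety, and propensity-score matching on baseline covariates does not address it.

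**Working it through.** **1. Can exposure-linked variables enter the score?** Having used E+P is constant in the training set, so it has no predictive value there and cannot be selected. Product, number of fills, days supply, recency and discontinuation vary among E+P users, are held in the HIRD, and are not excluded by the selection rule. They can enter.

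**2. Do their values carry over to Duavee?** A main-analysis Duavee user has no baseline E+P use and is censored at an E+P fill. A variable coded on E+P products is therefore structurally absent in her time at risk. If it were coded on the index drug, whichever that is, it would exist in both cohorts but could still be distributed differently.

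**3. Would a planned step show the problem?** Both record samples predate Duavee's launch, so neither can contain a Duavee user. Only PPV is estimated. Multiplying both cohorts' cases by one PPV leaves the rate ratio unchanged, because (PPV × rate in Duavee) / (PPV × rate in E+P) is the uncorrected ratio. PPV also carries no information on missed cases.

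**4. Scale, from Table 1 (year 3, hyperplasia).**

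Inputs: 399 E+P events; stated 95% CI (0.72, 1.39) at true HR 1.0 and (1.13, 1.99) at true HR 1.5.

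- SE of log HR = [ln(1.39) − ln(0.72)] / (2 × 1.96) = 0.168.
- Implied Duavee events = 1 / (0.168² − 1/399), which is 39.0 with the unrounded SE.
- Check at HR 1.5: SE = √[1/(1.5 × 39.0) + 1/399] = 0.140, giving (1.14, 1.97) against the stated (1.13, 1.99).

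The printed 5,400 users at 10 months each would give only 20.1 Duavee events and (0.64, 1.57). That mismatch is a separate matter. I use the 39.0 events that the stated interval implies.

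For a rare outcome with negligible false positives, observed HR = true HR × R, where R = sensitivity in Duavee / sensitivity in E+P. The protocol gives no sensitivities, so R is assumed:

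| R | True HR | Observed HR | 95% CI |
|---|---|---|---|
| 1.0 | 1.5 | 1.50 | 1.14–1.97 |
| 0.9 | 1.5 | 1.35 | 1.01–1.80 |
| 0.8 | 1.5 | 1.20 | 0.89–1.62 |
| 0.67 | 1.5 | about 1.0 | 0.72–1.40 |
| 1.25 | 1.0 | 1.25 | 0.93–1.68 |

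- The stated lower limit of 1.13 reaches 1.0 at R = 1/1.13 = 0.885.
- At R = 0.8 and true HR 1.5, the chance that the CI lies above 1 falls from about 82% to about 22%.
- With an equal false-positive rate in both cohorts, observed HR = true HR × R × PPV + (1 − PPV), where PPV is that in E+P users. At PPV 0.8, R = 0.8 and HR 1.5 this is 0.96 + 0.20 = 1.16, against 1.40 at R = 1.

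**5. What R might be (simulation, all inputs assumed).** Each run has 200 training women, half of them cases; one normal clinical predictor with a mean shift in cases; one binary E+P-fill predictor that is always 0 in Duavee users; a logistic score; and a Youden threshold. R is shown for log-odds of 0.5 / 1.0 / 1.5 on the fill predictor:

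| Clinical shift | Fill predictor in non-cases | R |
|---|---|---|
| 1.2 | about 40% | 0.91 / 0.76 / 0.59 |
| 1.2 | 30% | 0.93 / 0.82 / 0.65 |
| 2 | 30% | 0.97 / 0.93 / 0.86 |
| 3 | 30% | 0.99 / 0.97 / 0.95 |

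The loss runs from about 1% to about 41% of Duavee events. It is large only when clinical predictors are weak and the fill variable is strong and always zero for Duavee. This range is not a bound: at shift 1.2 with the predictor in 50% of non-cases, R falls to 0.53 at log-odds 1.5. If the E+P predictor lowers the score, R exceeds 1.

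**The case against.** The strongest reply is that this rests on silence, and that the list of candidate predictors belongs in the separate Endpoint Algorithm Development Plan, which is not shown. That plan could well contain the restriction. But Appendix 3 defers details of the validation process, while it states the selection rule itself: predictors come from the HIRD and are weighted empirically. It states that rule without the limit it needs, and it fixes development and validation in E+P users only.

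A second reply is that experts shape the initial algorithm around clinical markers of care, so a score driven by hormone fills is unlikely. This makes the problem less probable, but it does not restrict what the second, data-driven step may select.

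A third reply is that supply, recency and discontinuation could be coded for the index drug, since Section 7.3.1 defines exposure in the same way for both cohorts. That is right. It removes the always-zero case but not a difference in distribution.

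A reader might go further and infer that Duavee events will be under-detected and an excess risk hidden. The protocol does not support that. The bias arises only if a treatment variable is selected with real weight and takes different values by drug, and its direction is open. If the model settles on diagnosis, biopsy and surgery claims, sensitivity may be similar in the two cohorts. Nor does the text say that every HIRD variable will be offered to the model; it only sets no exclusion.

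**Conclusion.** The point holds as a matter of what the protocol permits. Equal detection of the primary endpoints in the two cohorts is not assured, because the score may draw on study-hormone dispensing and is built and validated without any Duavee user. The documents support saying that sensitivity could differ, not that it will.

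The size cannot be derived from the documents. The loss of about 1% to 40% of Duavee events comes from assumed predictor strengths, prevalences and coding, and the large values need weak clinical predictors together with an always-zero coding. Even a modest difference would matter, since a ratio of 0.885 removes the year-3 separation from 1 at a true HR of 1.5. The planned PPV correction could not bring such a difference to light. The point should be settled before the model is fitted.

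**What to change.** State in Appendix 3, and carry into the Endpoint Algorithm Development Plan, that candidate predictors for Algorithm 2 are limited to claims with the same meaning in both cohorts: disease diagnoses, diagnostic work-up, endometrial procedures, pathology, surgery and oncology care. State also that all Duavee, E+P and estrogen dispensing variables (product, fills, days supply, recency, discontinuation) are excluded from the model.

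The cost is a sentence or two of text and a possible small loss of discrimination in E+P users. No extra records need review. A test that the score stays the same when the index drug is relabelled adds little, because it would pass by construction once these variables are barred.

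The change does not deal with differences between cohorts in work-up or coding. Those would show only in records reviewed from both cohorts.
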